The objective of this pilot study is to determine if an experimental mouth rinse and a marketed dry mouth rinse are more effective in relieving dry mouth (as determined by the response to “relieving the discomfort of dry mouth” question from the modified Product Performance and Attributes Questionnaire I/ Moisturization and Dryness (PPAQ I/ MD)) compared to water.

2. Overall Study Design and Plan

This is a controlled, randomized, 3-treatment, 3-period crossover study in subjects with self-reported dry mouth symptoms as determined by subject responses to the Dry Mouth Inventory (DMI). A sufficient number of volunteers will be screened to ensure enrollment of up to 30 subjects at Acclimation. Subjects who meet the eligibility criteria will continue into the treatment phase of the study. Safety will be assessed by Oral examinations at Baseline/Day1 and Day 4. Subjects will complete questionnaires at Baseline (before product use Day 1 only), after immediate use, 30 minutes, 1 hour, 2 hours, and 4 hours after supervised product use on Day 1 and Day 4 of each period. The PPAQ II questionnaire will be completed in the morning of Day 4 of each period. Subjects will be randomly assigned to treatment sequences at the Baseline visit of Period 1. The treatment and washout periods will be repeated until all three treatment periods have been completed.

Table 1. Study Schedule by Procedure Type and Visit

Procedures	Screening/ Acclimation	Treatment Periods 1, 2, & 3					Washout
		Day 1 On site	Day 1 Off Site	Days 2 & 3 At Home	Day 4 On site	Day 4 Off Site	
Informed Consent	X						
Medical History	X						
Demographics	X						
DMI Questionnaire	X						
Inclusion/Exclusion	X						
Acclimation/Washout Product Distribution	X						
PPAQ II Questionnaire					X*		
Continuance Criteria		X			X		
Baseline MD Questionnaire		X					
Oral Examination		X			X		
Assigned Rinse / Water Product Distribution		X					
Supervised AM Product Use		X			X		
Immediate MD Questionnaire		X			X		
Product Usage Questionnaire		X**					
PPAQ I/ MD Questionnaire- 30 minutes		X			X		
PPAQ I/ MD Questionnaire- 1 hour			X			X	
PPAQ I/ MD Questionnaire- 2 hour			X			X	
PPAQ I/ MD Questionnaire- 4 hour			X			X	
4-hour Rating Questionnaire			X			X	

Product Diary		X	X	X	X		
Product Diary Return					X		
Treatment Product Return					X		
General Comments	X	X			X		
AEs		X			X		
Subject Accountability					X***		

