* PPAQ II will be completed at home immediately after wake-up; **This questionnaire will be analyzed outside of this protocol

***P3-Day 4 only or when subject is dismissed from study.

Screening/Acclimation Visit

At the site, up to forty subjects will be asked to read and sign an informed consent form and will receive a signed copy for their records. Personal medical history information will be reviewed and retained as site source documentation. Demographic information will be recorded, and subjects will answer the DMI questionnaire to ensure study eligibility. Entrance criteria will be assessed. At total of thirty qualifying subjects will receive acclimation products and usage instructions. Subjects continuing will begin using these products in place of their normal oral hygiene products for the duration of the study. They will be instructed to brush their teeth in the morning of Day 1 visit. Subjects not meeting study entrance criteria will be dismissed.

Treatment Visits, Periods 1-3

Day 1 On-site Visit

Continuance criteria will be assessed. Subjects will complete a Baseline MD Questionnaire, followed by an oral examination. Subjects will then be randomly assigned to a treatment sequence (Period 1 only). Assigned treatment product kit boxes will be distributed, written instructions reviewed, and subjects will use the assigned products for the first time under supervision by site staff. A timer will be set for 4 hours and subjects will be instructed to refrain from eating, drinking, smoking, using their test products, using tobacco, using a medicated lozenge, chewing gum, or breath mints during the 4-hour time period. Immediately following product use, subjects will complete an Immediate MD Questionnaire and Product Usage Questionnaire (analyzed outside of this protocol). Subjects will remain on-site for the first 30 minutes to complete the PPAQ I/ MD 30-minute Questionnaire. Subjects will be instructed to complete PPAQ I/ MD at 1-hour, 2-hour and 4-hour and to fill out the 4-hour Rating Questionnaire at 4-hour. Subjects who received rinse products will be reminded to use them at least one more time (up to 5 times daily) after the last 4-hour questionnaire for Day 1 has been completed. Subjects will be reminded to bring their treatment boxes to their next study visit, and to refrain from using any rinse product the morning of their site visit.

Day 1 Off-site

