Subjects will complete questionnaires, PPAQ I/ MD, at 1-hour (Day 1 PPAQ I/ MD 1h), 2-hour (Day 1 PPAQ I/ MD 2h), 4-hours (Day 1 PPAQ I/ MD 4h), and a 4-hour Day 1 Rating Questionnaire. Subjects will refrain from eating, drinking, smoking, using tobacco, using a medicated lozenge, chewing gum, or breath mints during the 4-hour time period until the last questionnaire for Day 1 has been completed.

All subjects will fill out a product diary tracking their product usage.

Days 2 and 3 At-home

Subjects will use the toothpaste products at home twice a day. Subjects that were assigned to the rinse products should use the rinse at least twice a day (no more than 5 times a day). All subjects will fill out a product diary tracking their product usage. Subjects will be reminded to follow the restrictions listed on the usage instructions. There is no eating or drinking restrictions for Day 2 and Day 3. Subjects from all groups will be allowed to sip unlimited amount of water.

Day 4 On-site Visit

Before coming to the site, subjects will complete a PPAQ II questionnaire (this questionnaire should be completed immediately after waking up). Subjects will also be sent a reminder to brush but not to use the assigned rinse product the morning, and to bring treatment products and the completed PPAQ II to their next site visit. Continuance criteria will be assessed, and take-home rinse products, product diaries and completed PPAQ II will be collected. An oral examination will be performed. After the oral exam, subjects will use the assigned products under supervision by site staff. A timer will be set for 4 hours. Subjects will remain on-site to complete the Immediate MD questionnaire and the 30-minute questionnaire (Day 4 PPAQ I/ MD 30 min). Subjects will be instructed to complete (Off-site) PPAQ I/ MD at 1-hour, 2-hour and 4-hour and to fill out the 4-hour Rating Questionnaire at 4-hour.

At this visit site staff will remind the subjects to refrain from eating, drinking, smoking, using any oral care products, using tobacco, using a medicated lozenge, chewing gum, or breath mints during the 4-hour time period. Subjects will be reminded to follow the restrictions listed on the usage instructions.

At Period 3 Day 4 washout product will be collected.

Day 4 Off-site

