6. Identity of Investigational Product(s)

- Acclimation/Washout: Burt's Bees Enamel Care Toothpaste (0.243% sodium fluoride, 0.13% w/v fluoride ion) and an Oral-B Indicator toothbrush
- Group 1: Burt's Bees Enamel Care Toothpaste (0.243% sodium fluoride, 0.13% w/v fluoride ion), Biotene Dry Mouth rinse (Purified Water, Glycerin, Xylitol, Sorbitol, Propylene Glycol, Poloxamer 407, Sodium Benzoate, Hydroxyethyl Cellulose, Methylparaben, Propylparaben, Flavor, Sodium Phosphate, Disodium Phosphate), and an Oral-B Indicator toothbrush
- Group 2: Burt's Bees Enamel Care Toothpaste (0.243% sodium fluoride, 0.13% w/v fluoride ion), Experimental mouth rinse (0.1% Sodium Hyaluronate), and an Oral-B Indicator toothbrush
- Group 3: Burt's Bees Enamel Care Toothpaste (0.243% sodium fluoride, 0.13% w/v fluoride ion), 15ml of water (on-site only) and an Oral-B Indicator toothbrush

7. Product Usage

At-home Toothpaste

Subjects will brush their teeth thoroughly, twice daily (morning and evening) as they normally do with the provided toothpaste and toothbrush. Subjects will be asked to use this toothpaste and toothbrush for the duration of the study, for both the acclimation/washout and treatment periods. Flossing and tongue brushing are permitted during the study if it is part of their normal routine.

Group 1 - Marketed rinse

On-site: Subjects will rinse their mouth with the assigned mouth rinse 15 ml for 30 seconds. Subjects will record usage in their product diaries. Subjects will not be allowed to use any mouth rinse during the 4-hour time period on Day 1 and Day 4.

At-home: Subjects will be instructed to use the rinse products at least twice a day and up to 5 times a day including any on-site usage, 15 ml for 30 seconds. Rinse can be used alone or after each time subjects brush. Subjects will record the usage in their product diaries.

Group 2 - Experimental mouth rinse

On-site: Subjects will rinse their mouth with the assigned mouth rinse 15 ml for 30 seconds. Subjects will record usage in their product diaries. Subjects will not be allowed to use any mouth rinse during the 4-hour time period on Day 1 and Day 4.

At-home: Subjects will be instructed to use the rinse products at least twice a day and to 5 times a day including any on-site usage, 15 ml for 30 seconds. Rinse can be used alone or after each time subjects brush. Subjects will record the usage in their product diaries.

Group 3 – Water/ No Rinse

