On-site: Subjects will take, all at one time, a 15ml sip of water.

At-home: Subjects will continue brushing with provided washout toothpaste. Subjects will not be allowed to use any mouth rinse. Subjects will record their toothpaste usage in their product diaries.

8. Blinding, Labeling, and Shipping Plan

Acclimation/Washout take-home kit boxes will be labeled with study number, emergency phone number, distributor name/address, appropriate caution statements, content statement and other information as required by internal regulations and clinical SOPs. Treatment take-home kit boxes will be identically sized and labeled with a unique kit box number or code, study number, emergency phone number, distributor name/address, appropriate caution statements, content statement and other information as required by internal regulations and clinical SOPs. The shipping containers will be labeled with the clinical site address and a content statement listing study number and kit box numbers contained within. The site will be provided with a randomization treatment sequence and supplemental product.

The site will be provided with a code breaker report in a sealed envelope. The sealed code breaker report contains documents that list the kit box number or treatment code while the identity of the treatment products is hidden by an opaque scratch-off seal. If the study blind needs to be broken, an individual subject's investigational product may be ascertained by opening the sealed code breaker report, locating the subject's kit box number or treatment code and scratching off the opaque seal to reveal the treatment identity. The sealed code breaker report will be opened if a clinically serious AE occurs or management of the subject requires knowledge of the identity of the investigational product. The Investigator should immediately inform the Sponsor that the code will be broken and record the date, time and reason for breaking the code in writing. After the study is complete and the study database has been finalized and locked, the site will return the code breaker report to the Sponsor using the self-addressed, stamped envelope provided by the Sponsor.

9. Method of Assigning Subjects to Treatment Groups

Study Design	N	# of Treatments	# of Periods	Treatment Sequences	Number of Subjects Per Sequence
Crossover	30	3	3	ABC, ACB, BAC, BCA, CAB, CBA	5-6

Treatment Sequence Schedule

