Since you have been used the product, please rate each of the following at this timepoint: (Select one response for each attribute)- excellent=5, very good=4, good=3, fair=2, poor=1:

- 1) Relieves the discomfort of your dry mouth
- 2) Feels comfortable in your mouth
- 3) Soothes your mouth
- 4) Allows you to speak without difficulty
- 5) Effectively moistens your mouth
- 6) Effectively lubricates your mouth
- 7) Helps to freshen your breath
- 8) Protects your mouth from drying out
- 9) Provides whole mouth comfort
- 10) Helps you to swallow without difficulty
- 11) Helps your mouth feel "normal"

Subjects must answer:

- 1) How moist does your mouth feel now? (0=not at all to 10= very moist)
- 2) How dry does your mouth feel now? (0=very dry to 10=not dry at all)

PPAQ II Questionnaire

Since you have been using the product over the last 4 days, please rate each of the following as they apply to the rinse study product: (Select one response for each attribute)- excellent=5, very good=4, good=3, fair=2, poor=1:

- 1) Provides relief all night
- 2) Reduces the number of times you wake up from dry mouth
- 3) Feeling less parched when you wake up
- 4) Having a long-lasting dry mouth relief

- 5) Having a long-lasting lubricating effect
- 6) Having a long-lasting moisturizing effect

4-hour Rating Questionnaire

- 1) How would you rate the overall moisturization of your mouth after using the product? 0= does not provide moisturization at all to 10=best possible moisturization
- 2) How would you rate the long-lasting moisturization effect of the product? 0= does not provide long lasting moisturization at all to 10=best possible long lasting moisturization
- 3) How would you rate the overall relief of your dry mouth after using the product? 0= does not provide relief at all to 10=best possible relief
- 4) How would you rate the long-lasting dry mouth relief of the product? 0= does not provide long lasting relief at all to 10=best possible long-lasting relief

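### PPAQ II asks for ratings of a rinse in the Water/No Rinse period, where there is none, so the Water value in all 12 planned PPAQ II tests has no single meaning

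*Combined protocol and SAP*

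**What the plan says.** **The form.** The PPAQ II stem in Appendix II has a four-day recall and tells subjects to "please rate each of the following as they apply to the rinse study product". There are six items, each scored from excellent (5) to poor (1), with no not-applicable option. No separate wording is listed for the Water period.

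**When it is given.** Section 2 states: "The PPAQ II questionnaire will be completed in the morning of Day 4 of each period". The footnote to Table 1 adds: "PPAQ II will be completed at home immediately after wake-up". The Day 4 On-site Visit text agrees: "this questionnaire should be completed immediately after waking up". The form therefore precedes the Day 4 supervised use, and the Water period is not exempt.

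**What the Water period contains.** Section 6 lists the Group 3 test product as "15ml of water (on-site only". Section 7 heads the group Water/No Rinse and says "On-site: Subjects will take, all at one time, a 15ml sip of water". For Group 3 at home it says "Subjects will not be allowed to use any mouth rinse".

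**What a rinse period contains.** After the first supervised use, the Day 1 text says "Subjects who received rinse products will be reminded to use them at least one more time (up to 5 times daily". On Days 2 and 3 the rinse is used two to five times a day.

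**What is tested.** Section 12 applies two hypotheses to each PPAQ II question: Experimental rinse against Water, and Marketed rinse against Water. It lists no comparison between the two rinses. PPAQ II responses are of secondary interest.

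**The concern.** A treatment contrast on a rating scale assumes that the same question was answered in each period. In a rinse period the PPAQ II question is clear: how well did the rinse perform? In the Water period the object named in the question does not exist, and the form does not say what replaces it. The documents leave at least four responses open: a rating of the Day 1 sip, a rating of the toothpaste (the one assigned product used throughout, and identical in all periods), a blank, or a reflex score of poor. These do not measure the same thing.

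The Water mean would then depend partly on how subjects resolve the wording, and every planned PPAQ II contrast uses that mean. Default scores of poor would widen the rinse-minus-Water difference. Ratings of a well-liked toothpaste would narrow it. Blanks would leave the contrast resting on the subjects who chose to answer. A difference found at the two-sided 0.10 level could not be attributed cleanly to the rinse.

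This matters most for night-time and waking relief, because PPAQ II is the only form completed on waking.

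**Working it through.** The plan gives no figure for this point, so the check is a count from its own rules.

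**1. Planned PPAQ II tests.** Inputs: 6 items (Appendix II), 2 comparisons (Section 12), 1 time point per period (Section 2).
- 6 x 2 x 1 = 12 tests, all against Water.
- Items 1 to 3 concern the night or waking: 3 x 2 = 6 tests. Items 4 to 6 concern long-lasting effects in general: 3 x 2 = 6 tests.

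**2. Share of all planned tests.** Inputs: item counts from Appendix II; times and days from Table 1.

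| Form | Count | Tests |
|---|---|---|
| PPAQ I | 11 items x 4 times x 2 days x 2 comparisons | 176 |
| MD items on the same form | 2 x 4 x 2 x 2 | 32 |
| 4-hour Rating | 4 x 2 x 2 | 16 |
| PPAQ II | 6 x 1 x 2 | 12 |
| Total | 176 + 32 + 16 + 12 | 236 |

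12 / 236 = 5.1%. If the Immediate MD form is also counted (2 x 2 x 2 = 8), the total is 244 and the share is 12 / 244 = 4.9%.

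**3. Assigned test exposure before PPAQ II.** Rinse is barred on the morning of Day 4, so only Days 1 to 3 count.

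| Day | Rinse period | Water period |
|---|---|---|
| 1 | 2 to 5 uses (one supervised, at least one more) | one 15 ml sip |
| 2 | 2 to 5 uses | none |
| 3 | 2 to 5 uses | none |
| Total | 6 to 15 rinse uses | 0 rinse uses, 1 sip |

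The second supervised sip comes after PPAQ II. Free sipping of water on Days 2 and 3 is allowed in all groups, so it is not counted.

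**4. How the wording can move the contrast.** Suppose a share p of Water-period subjects enter 1 by default when a clear question would have drawn a score w. The Water mean falls by p x (w - 1), and each rinse-minus-Water difference rises by the same amount. The documents give neither p nor w. Other readings of the form push the other way, so neither the size nor the direction can be stated.

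**The case against.** **The control is defined, and a sensible reading exists.** Section 12 names Water as the comparator, the stem also speaks of the product, and the subject was handed 15 ml of water under supervision. Rating that water is plausible. This stands against two stronger claims that a reader might infer: that a subject who follows the form can only score a rinse never received or leave a blank, and that the PPAQ II contrasts have no control. The documents support neither. What is undefined is the object being rated.

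**Staff can explain the form.** Completion at home might suggest that nobody can clarify the wording. That goes too far. Written instructions are reviewed on Day 1, a reminder mentioning PPAQ II is sent before the Day 4 visit, and the form is collected that day. The usage instructions and CRFs are separate documents not included here, so Water-specific wording there can be neither assumed nor excluded. But the listed form is inapplicable as written, and no instruction in the protocol resolves it.

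**The overnight comparison is not lost.** This is right. Answers will be collected; their interpretation is in doubt. Only items 1 to 3 are specific to night or waking. Two of the 4-hour Rating items ask about long-lasting moisturization and relief in all periods, over a shorter horizon than items 4 to 6.

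**A one-line instruction to rate the water would do.** It would settle the referent. It would still ask for a several-day, overnight rating of one sip taken three mornings earlier, under a stem that says rinse.

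**This is a pilot, and the tests are secondary.** True, and it limits the weight of the point. It does not remove it, because the wording affects every planned PPAQ II test and is easy to change before data collection.

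**Conclusion.** The point holds as an ambiguity in what is rated, and it is worth fixing before data collection. All 12 planned PPAQ II tests, about 5% of the planned total, compare a rinse with a Water answer that has no single referent. Six of the 12 involve the only overnight or waking items. These contrasts may partly reflect the form rather than the treatment.

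This rests on the questionnaire wording as listed in Appendix II and on no Water-specific instruction being given elsewhere. The mismatch and the counts follow directly from the text. The effect on the data is a possibility that the documents do not let anyone measure.

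A reader might extend the problem to the primary endpoint, since PPAQ I/ MD is also used in the Water period. The documents do not support that. The PPAQ I/ MD stem refers to the product without calling it a rinse, and the primary response is taken two hours after a supervised use on Day 4. The 0-10 moistness and dryness items name no product at all.

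**What to change.** Reconcile Appendix II with Sections 7 and 12 before data collection. No regimen change is needed.

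**Recommended route.** Give PPAQ II one stem that applies in all three periods and names no rinse, for example: *Thinking about your mouth since Day 1 of this study period, please rate each of the following.* Reword the six items only as far as needed so that they do not presuppose a rinse. Item 1 could become *Relief from dry mouth all night*. Items 2 and 3 are phrased as improvements and need recasting as states, such as *Sleeping without waking from dry mouth*. Items 4 to 6 should stay general and not be narrowed to the night. Keep the five-point scale and the 12 tests. Add to Section 13 that blanks stay missing and that the number of blanks per item is reported by treatment.

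*Cost:* one stem, six small rewordings and one line of analysis text, with no added visit or form. The form moves from rating a product to rating the state of the mouth, so results are somewhat less comparable with other uses of PPAQ II.

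**If the product-rating wording must be kept.** Collect PPAQ II in the two rinse periods only, report it descriptively, and amend Section 2, Table 1 and Section 12 to remove it from the tests against Water.

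*Cost:* the 12 secondary tests are given up (236 - 12 = 224 remain, or 244 - 12 = 232 with the Immediate MD form), and with them the planned overnight and waking comparison with Water.
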